9.2 Exclusion Criteria

Subjects who meet any one of the following criteria (Table 9.2-1) cannot be included in this study or will be excluded from this clinical study. No vulnerable populations will be enrolled in this study per the local standard of care at the institution/IRB.

Table 9.2-1: Exclusion Criteria

Exclusion Criteria

- 1. Subjects who are currently enrolled in another investigational study that would directly interfere with the current study, without prior written approval from the sponsor
- 2. Subjects who the investigator deems at risk for study device or procedure related complications per the Instructions for Use (IFU) where commercially available or the Investigator Brochure (IB) for countries where the study device is not approved.

10 Subject Accountability

10.1 Point of Enrollment

Subjects will be considered enrolled into the study at the time of the study-specific Informed Consent Form (ICF) execution. Subjects who have signed informed consent but do not undergo the study procedure are considered screen failures. Screen failures will be recorded

in the Electronic Data Capture (EDC) system by each study site and will not count toward total study enrollment.

In the case it is determined that the subject failed to meet the inclusion/exclusion criteria after the subject has agreed to participate in the study and has signed the informed consent, the study personnel will complete the Screening form and the End of Study form.

10.2 Withdrawal

Subjects will participate in the study voluntarily and may withdraw at any time without prejudice to further treatment. All subjects enrolled in the clinical study (including those withdrawn from the clinical study) shall be accounted for and documented. If a subject withdraws from the clinical investigation, the reason(s) shall be reported. If such withdrawal is due to problems related to study device safety or performance, the investigator shall ask for the subject's permission to follow his/her status/condition outside of the clinical study.

Applicable case report forms up to the point of subject withdrawal, including an End of Study form must be completed. Unless the withdrawal is due to a Serious Adverse Event, additional subject data will not be collected after the point at which the subject has been withdrawn or withdraws consent from the study. Data collected up to the point of withdrawal may be used by the investigators as permitted in the ICF.

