11.6 Study Procedure

During the index procedure, the endoscopist or designated member of study staff will record: Clip information, and any activities completed or attempted during the procedure, regardless of original intent. Any ensuing adverse or device events will be recorded and reported.

11.7 30 Day (± 5 days) Telephone Interview Assessments

All enrolled subjects will be evaluated via telephone to screen for any post-procedure adverse events, and to evaluate the resolution of any previously noted adverse events or sequelae, as applicable.

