11.8 Study Completion

Subjects will be followed for 30 days (\pm 5 days) post index procedure. Subjects will continue to receive care from their doctor as they normally would. At study completion, an End of Study form will be completed, indicating whether the subject completed the study. If the last follow-up visit was not completed, the reason will be noted on the study completion form (e.g. subject withdrawn by investigator, subject withdrew consent, lost to follow-up, AE, death, etc.) and a Protocol Deviation form will be completed.

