19.1 Reportable Events by investigational site to Boston Scientific

It is the responsibility of the investigator to assess and report to BSC any event which occurs in any of following categories:

- All Non-Serious Adverse Events related to the Study Device and/or Study Procedure
- All Serious Adverse Events including those related to the Study Device and/or Study Procedure
- All events with a Fatal Outcome
- All Device Deficiencies
- Unanticipated Adverse Device Effects/Unanticipated Serious Adverse Device Effects
- New findings/updates in relation to already reported events

When possible, the medical diagnosis should be reported as the Event Term instead of individual symptoms.

If it is unclear whether or not an event fits one of the above categories, or if the event cannot be isolated from the device or procedure, it should be submitted as an adverse event and/or device deficiency.

Any reportable event, experienced by the study subject after informed consent, whether prior to, during or subsequent to the procedure, must be recorded in the eCRF.

Underlying diseases and chronic conditions are not reported as AEs unless there is an increase in severity or frequency during the course of the investigation. Death should not be recorded as an AE, but should only be reflected as an outcome of one (1) specific SAE (see Table 19.2-1 for AE definitions).

Refer to Instructions for Use or Investigator Brochure for the known risks associated with the device(s).

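### Protocol 10.2 ends study data collection at any withdrawal not due to an SAE, even when consent stands, so outcomes first arising between that withdrawal and day 30 are lost

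*Protocol*

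**What the plan says.** Protocol 10.2 sets the rule: "Unless the withdrawal is due to a Serious Adverse Event, additional subject data will not be collected after the point at which the subject" leaves, whether removed by someone else or by revoking consent. The only exception is a withdrawal caused by an SAE.

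For a subject who withdraws because of a problem with device safety or performance, the same section adds that "the investigator shall ask for the subject's permission to follow his/her status/condition outside of the clinical study". It does not say whether what is learned there may be entered or analysed.

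Section 10.2 also protects what came earlier: "Applicable case report forms up to the point of subject withdrawal, including an End of Study form must be completed", and "Data collected up to the point of withdrawal may be used by the investigators as permitted in the ICF".

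Three other sections bear on the point:
- Section 11.7 says "All enrolled subjects will be evaluated via telephone to screen for any post-procedure adverse events".
- Section 11.8 lists the reasons for a missed last visit as "subject withdrawn by investigator, subject withdrew consent, lost to follow-up, AE, death, etc", so withdrawal by the investigator and withdrawal of consent are separate categories.
- Section 19.1 makes reportable "All Serious Adverse Events including those related to the Study Device and/or Study Procedure" and "All Device Deficiencies".

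The SAP (7.3) has a rule for missing AE onset dates. It has none for a missing 30-day outcome, and SAP 4.1 does not say which analysis set is primary.

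**The concern.** The primary effectiveness endpoint runs to day 30, and the only scheduled contact after the procedure is one telephone call. The clip is placed once. When a subject is withdrawn by the investigator but has not revoked consent, respect for consent gives no reason to drop that call.

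Take a subject who leaves over a suspected device problem that is not an SAE and then bleeds, or loses closure, on day 12. Under 10.2 that outcome is not study data. Such subjects plausibly carry a higher risk of failure than the rest, so the missingness could be related to outcome. Both primary tests compare one arm with a fixed goal, and no control group shares the loss. If failures are lost more often than successes, the observed success rate rises and the test passes too easily. A related SAE that first arises after a non-SAE withdrawal is exposed in the same way: 19.1 wants it reported, but 10.2 has stopped collection.

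**Working it through.** **1. What is lost and what is kept under 10.2**

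| Situation | Study data after withdrawal? |
|---|---|
| Event recorded before withdrawal, including the one that prompted it | Already recorded and usable |
| Withdrawal due to an SAE | Collection may continue |
| Subject revokes consent, no SAE | None |
| Investigator withdraws subject, consent intact, no SAE | None, although 11.7 requires the call |
| Subject leaves over a device problem, no SAE | None; follow-up outside the study if permitted |
| Subject leaves over a device problem that is also an SAE | One sentence allows collection in the study, another points outside it |

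The loss is limited to outcomes that first arise after a non-SAE withdrawal and before day 30.

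**2. The plan's own figure**

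Inputs from Protocol 12.1.1.3 and SAP 3.1.3: goal 89%, expected success 94%, exact test, alpha 0.05, 217 subjects, raised to 240 for 10% attrition. The hypotheses are one-directional, so I take alpha as one-sided.

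The critical value r(n) is the smallest r with P(X ≥ r) ≤ 0.05 for X ~ Bin(n, 0.89).
- n = 217: r = 201 (p = 0.0492; 200 successes give p = 0.0788). Power at 94% is 84.1%. The stated power of at least 80% is reproduced.
- n = 240: r = 222 (p = 0.0462).
- Attrition: 217/0.9 = 241.1 and 217 × 1.1 = 238.7, so 240 is consistent with the plan. The allowance is 240 − 217 = 23 subjects.

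**3. How few subjects matter**

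221/240 gives p = 0.073 and misses the goal. With one failure removed from the denominator, 221/239 gives p = 0.048 and meets it.

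**4. False-pass probability under assumed loss**

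Assumptions, none of them in the documents: true success is exactly 89%; each failure is lost with probability f and each success with probability g; lost subjects leave the denominator.

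- Share observed: q = 0.89(1 − g) + 0.11(1 − f)
- Success rate among those observed: p* = 0.89(1 − g)/q
- False-pass probability: sum over n of P(Bin(240, q) = n) × P(Bin(n, p*) ≥ r(n))

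| f (failures lost) | g (successes lost) | Failures lost, 240 × 0.11 × f | p* | False pass, one-sided 0.05 |
|---|---|---|---|---|
| 0 | 0 | 0 | 89.0% | 4.6% |
| 10% | 10% | 2.6 | 89.0% | 3.9% |
| 10% | 0 | 2.6 | 90.0% | 9.4% |
| 20% | 10% | 5.3 | 90.1% | 10.4% |
| 20% | 0 | 5.3 | 91.0% | 20.9% |

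Equal loss does no harm; the dip from 4.6% to 3.9% reflects the discreteness of the exact test. The inflation comes from the difference between f and g.

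**The case against.** The strongest reply is that the exposure is small and already guarded.

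- SAE withdrawals are exempt, and related SAEs are the primary safety endpoint.
- A failure that prompts withdrawal is on the CRF before collection stops, and a clip problem seen by then is reportable as a device deficiency.
- A missed last visit requires a deviation form (11.8), and the sponsor reviews deviations on an ongoing basis (section 14).
- Participation after the procedure is a single call, so few subjects may withdraw at all.

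All of this stands and limits the point to late outcomes after non-SAE withdrawals. It does not remove it: a deviation form records that the outcome is missing but does not supply it.

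A reader might infer more than the text supports:
- **That likely failures never reach the primary endpoints.** The SAE exemption and the retention of earlier data contradict this.
- **That device-problem subjects are diverted out of the study.** The sentence concerns subjects who choose to leave, and asks for contact that would otherwise end. Its weakness is that the resulting information has no route into the analysis.
- **That investigators may withdraw subjects at will.** No passage grants this; investigator withdrawal appears only in the wording of 10.2 and among the example reasons in 10.4 and 11.8.
- **That the false-pass rate is about 9% or 21%.** Those values assume that only failures are lost. They also assume that lost subjects leave the denominator, which neither document says; counting missing outcomes as failures would remove this inflation.
- **That the 10% attrition allowance measures the problem.** It is not attributed to withdrawal, and loss to follow-up (10.3) is a separate route.

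It can also be said that the two sentences on SAE and device-problem withdrawals are compatible, since both could apply to one subject. That is possible, but the text does not say so.

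**Conclusion.** The point holds in limited form. Section 10.2 applies one stop rule to two different situations, and for investigator withdrawal with consent intact it overrides the 30-day call in 11.7 without a stated reason. For subjects leaving over a device problem, permission is sought only for follow-up that the analysis cannot use. Where such a withdrawal is also an SAE, the two sentences should be reconciled.

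The direction of bias is toward passing only if failures are lost more often than successes, which is plausible but not shown. Its size cannot be derived from the documents. Under the stated assumptions the false-pass probability for effectiveness lies between 3.9% and 20.9%, against 4.6% with no loss. I give no figure for safety, where the SAE exemption should make the loss smaller. Because a single dropped failure can change a borderline result and the remedy is cheap, the change should be made.

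**What to change.** Amend Protocol 10.2 as follows:
1. Data collection ends only when the subject withdraws consent to further data collection.
2. A subject withdrawn by the investigator keeps the 30-day contact and SAE collection.
3. A subject leaving because of a device safety or performance problem is asked to allow the 30-day contact as study data, in place of follow-up outside the study. The text should say how this applies when the problem is also an SAE.
4. Where permission is given, the data are entered in the EDC and counted in both primary endpoints.

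Subjects who refuse will still lack an outcome. A SAP rule for missing 30-day outcomes would complement this change but not replace it, because collecting the outcome is better than imputing it.

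The cost is a protocol amendment with matching ICF wording and at most one telephone call per withdrawn subject. The observed success rate may come out slightly lower.

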10.3 Lost to Follow-Up

A subject will be considered lost to follow-up if he/she fails to return for their scheduled follow-up visits and is unable to be contacted by the study site staff after at least three documented attempts, at which point an End of Study form should be completed. Before a participant is deemed lost to follow up, the investigator or designee will make every effort to regain contact with the participant (where possible, 3 telephone calls and, if necessary, a certified letter to the participant's last known mailing address or local equivalent methods). These contact attempts should be documented in the participant's medical record or study file.

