12.1.1.3 Hypotheses and Sample Size Justification

Initial cohort:

No hypotheses will be tested, only observational, summary statistics will be performed.

Continued enrollment cohort:

A systematic literature search was conducted on PubMed and Embase from January 1, 2016 to September 2022 to identify studies that evaluated the safety and effectiveness of an endoscopic clip device for closing various types of incisions, lesions, or defects in the gastrointestinal tract resulting from endoscopic mucosal resection (EMR), endoscopic submucosal dissection (ESD), polypectomy of polyps or adenomas, perforations, and fistulas. The primary objective of the search strategy was to identify studies that examined the closure of large mucosal defects by endoscopic clipping. Twenty studies were identified through a post-market literature review activity were included to the analysis with a total of 2257 patients.

We hypothesize that the **clinical success rate** of MANTISTM clip will be greater than the performance goal of **89%** with expected clinical success rate of **94%**. These assumptions are based in the following meta-analyses of clinical success for closure of a defect:

• 20 publications representing 2257 patients: 93.9% (95% CI 88.6%-97.6%)

We hypothesize that the **serious adverse event (SAE) rate** related to MANTISTM clip or the endoscopic clipping portion of the procedure will be lower than the performance goal of **19%** with expected related SAE rate of **10%**. These assumptions are based in the following meta-analyses of clinical success for closure of a defect:

- 9 publications representing 1019 patients: 9.8% (95% CI 3.7%-18.5%)
 - 12.2 Using an exact test with an alpha level of 0.05, 217 subjects enrolled will provide at least 80% power for the performance and safety metrics. An additional 10% will be added for attrition, so total enrollment will be 240 subjects. These tests will only be performed for cases in the continued enrollment cohort General Statistical Methods

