	2. Subjects who the investigator deems at risk for study device or procedure related complications per the Instructions for Use (IFU), where commercially available or the Investigator Brochure (IB) for countries where the study device is not approved.	

MANTIS Clip Study

Statistical Methods

Initial cohort:

No hypotheses will be tested, only observational, summary statistics will be performed.

Continued enrollment cohort:

A systematic literature search was conducted on PubMed and Embase from January 1, 2016 to September 2022 to identify studies that evaluated the safety and effectiveness of an endoscopic clip device for closing various types of incisions, lesions, or defects in the gastrointestinal tract resulting from endoscopic mucosal resection (EMR), endoscopic submucosal dissection (ESD), polypectomy of polyps or adenomas, perforations, and fistulas. The primary objective of the search strategy was to identify studies that examined the closure of large mucosal defects by endoscopic clipping. Twenty studies were identified through a post-market literature review activity were included to the analysis with a total of 2257 patients.

We hypothesize that the **clinical success rate** of MANTISTM clip will be greater than the performance goal of 89% with expected clinical success rate of 94%. These assumptions are based in the following meta-analyses of clinical success for closure of a defect:

20 publications representing 2257 patients: 93.9% (95% CI 88.6%-97.6%)

We hypothesize that the serious adverse event (SAE) rate related to MANTISTM clip or the endoscopic clipping portion of the procedure will be lower than the performance goal of 19% with expected related SAE rate of 10%. These assumptions are based in the following meta-analyses of clinical success for closure of a defect:

9 publications representing 1019 patients: 9.8% (95% CI 3.7%-18.5%)

Using an exact test with an alpha level of 0.05, 240 subjects enrolled will provide at least 80% power for the performance and safety metrics. These tests will only be performed for cases in the continued enrollment cohort.

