3.1.3 Hypotheses and Sample Size

Initial cohort:

No hypotheses will be tested, only observational, summary statistics will be performed.

Continued enrollment cohort:

A systematic literature search was conducted on PubMed and Embase from January 1, 2016 to September 2022 to identify studies that evaluated the safety and effectiveness of an endoscopic clip device for closing various types of incisions, lesions, or defects in the gastrointestinal tract resulting from endoscopic mucosal resection (EMR), endoscopic submucosal dissection (ESD), polypectomy of polyps or adenomas, perforations, and fistulas. The primary objective of the search strategy was to identify studies that examined the closure of large mucosal defects by endoscopic clipping. Twenty studies

were identified through a post-market literature review activity were included to the analysis with a total of 2257 patients.

We hypothesize that the **clinical success rate** of MANTISTM clip will be greater than the performance goal of **89%** with expected clinical success rate of **94%**. These assumptions are based in the following meta-analyses of clinical success for closure of a defect:

• 20 publications representing 2257 patients: 93.9% (95% CI 88.6%-97.6%)

The null and alternative hypotheses for the primary effectiveness endpoint are as follows:

Ho: $\pi_1 \le 89\%$ *Ha*: $\pi_1 > 89\%$

where π_1 is the probability of clinical success.

We hypothesize that the **serious adverse event (SAE) rate** related to MANTISTM clip or the endoscopic clipping portion of the procedure will be lower than the performance goal of **19%** with expected related SAE rate of **10%**. These assumptions are based in the following meta-analyses of clinical success for closure of a defect:

• 9 publications representing 1019 patients: 9.8% (95% CI 3.7%-18.5%)

The null and alternative hypotheses for the primary endpoint are as follows:

Ho: $\pi_1 \ge 19\%$ *Ha*: $\pi_1 < 19\%$

where π_1 is the probability of an related SAE.

Using an exact test with an alpha level of 0.05, 217 subjects enrolled will provide at least 80% power for the performance and safety metrics. An additional 10% will be added for attrition, so total enrollment will be 240 subjects. These tests will only be performed for cases in the continued enrollment cohort

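### Section 10.3 requires no medical-record or vital-status check before a subject is deemed lost to follow-up, so primary endpoint events unknown to the site may be missed in an outcome-dependent way

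*Protocol*

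**What the plan says.** Protocol 8.1 and 11.7 make a telephone interview at 30 days (± 5) the only scheduled contact after the procedure. Both primary endpoints of the continued enrollment cohort depend on what is known by then: delayed bleeding and sustained closure for effectiveness, and related SAEs for safety.

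Protocol 10.3 declares a subject lost when follow-up is missed and the subject "is unable to be contacted by the study site staff after at least three documented attempts"; the End of Study form is then completed. The effort required beforehand is "where possible, 3 telephone calls and, if necessary, a certified letter to the participant's last known mailing address", or a local equivalent. The medical record appears in 10.3 only as a place to note the attempts.

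Other sections bear on the point:
- **11.8** says "Subjects will continue to receive care from their doctor as they normally would", so records of routine care will normally exist.
- **10.4 and 11.8** ask for the reason a last visit was missed. AE, death and lost to follow-up are separate options.
- **19.1 and 19.4** require all SAEs and all fatal events to be reported, on timelines that run from when the site becomes aware.
- **21.1** has monitors reviewing source documents.
- **10.2** stops data collection after withdrawal unless the withdrawal is due to an SAE.

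On sample size, Protocol 12.1.1.3 adds: "An additional 10% will be added for attrition, so total enrollment will be 240 subjects". Neither document says how a subject without a 30-day outcome enters either primary analysis.

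**The concern.** A subject who has been readmitted with bleeding or a perforation, or who has died, is less likely to answer the telephone than one who is well. Non-response can therefore depend on the outcome being measured. If the site looks no further, the analysed subjects are weighted towards those well enough to answer, and both observed rates lean towards success.

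The events concerned (delayed bleeding, re-intervention, related SAEs) are mostly medically attended and would often be found in a chart or through the treating physician. The planned attrition of about 23 subjects exceeds the 16 failures that the effectiveness test tolerates at 217 subjects, so what happened to the lost group could matter.

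**Working it through.** **Inputs.** From the documents: exact test, alpha 0.05, 217 evaluable and 240 enrolled (Protocol 12.1.1.3; SAP 3.1.3); effectiveness goal 89% and expected 94%; safety goal 19% and expected 10%; directional hypotheses (SAP 3.1.3), hence one-sided tests. Assumed: the event rate among lost subjects, which neither document gives and which is shown as a range; and a complete-case analysis, since the plan states no rule.

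**1. The plan's own figure.** The plan states: "Using an exact test with an alpha level of 0.05, 217 subjects enrolled will provide at least 80% power". With X failures ~ Binomial(217, 0.11) under the effectiveness null:
- P(X ≤ 16) = 0.0492 and P(X ≤ 17) = 0.0788, so the test passes with at most 16 failures (at least 201 successes).
- Power at 6% failures: P(X ≤ 16) = 84.1%.
- Safety: it passes with at most 31 subjects with a related SAE (exact alpha 0.0426); power at 10% is 98.3%.

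Both meet the 80% claim at one-sided 0.05. At one-sided 0.025, effectiveness power would be 67.6%, so 0.05 is used throughout.

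**2. Size of the lost group.** 240 − 217 = 23. This is an upper bound on unreachable subjects, because attrition also covers withdrawals.

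**3. Results at the expected rates.**
- Effectiveness: 217 × 6% = 13.0 failures among those reached. If the lost fail at 2 to 3 times 6%: 23 × 12% = 2.8 and 23 × 18% = 4.1, so about 3 to 4 unseen. Recovered subjects enter the denominator as well as the numerator: 13 + 3 to 4 = 16 to 17 of 240. Against 89%, p = 0.016 to 0.028, which passes.
- Safety: 217 × 10% ≈ 22. At 2 to 3 times 10%: 23 × 20% = 4.6 and 23 × 30% = 6.9, so about 5 to 7 more. That gives 27 to 29 of 240, against a limit of 35 at n = 240, which passes.

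**4. Borderline result.** The effectiveness limit at n = 240 is 18 failures (p = 0.046); 19 gives p = 0.073 and 20 gives p = 0.109.
- Observed 16 of 217 passes (p = 0.049).
- If the lost fail at the observed rate: 23 × 16/217 = 1.7, about 2; 18 of 240 still passes.
- If the lost contribute 3 to 4 failures, as in step 3: 19 to 20 of 240 does not pass.

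**5. Type I error when the device is exactly at the goal.** Fix the overall rate at the goal, assume rate f among 23 lost, and apply the 217-subject limits to those reached.
- Effectiveness: failure rate among those reached = (240 × 0.11 − 23f)/217. Safety: (240 × 0.19 − 23f)/217.

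| Endpoint | f among the lost | Rate among those reached | Type I error |
|---|---|---|---|
| Effectiveness | 11% (loss unrelated to outcome) | 11.0% | 4.9% |
| Effectiveness | 20% | 10.05% | 11.3% |
| Effectiveness | 30% | 8.99% | 24.3% |
| Safety | 19% (loss unrelated to outcome) | 19.0% | 4.3% |
| Safety | 30% | 17.8% | 9.8% |
| Safety | 40% | 16.8% | 18.8% |

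**The case against.** The best defence is that the protocol already covers much of this. Section 10.3 asks for every effort and allows local equivalents; 10.4 requires a reason for non-completion, with death and AE listed apart from loss; 19.1 requires SAEs and deaths to be reported whether or not the call is answered; monitors review source documents. What remains is mainly care given elsewhere, where the site's own chart is least informative. And at the expected rates neither conclusion moves.

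Most of this stands, and it rules out several stronger readings that a reader might infer:
- **That the protocol directs close-out without a record check.** It is silent on one; it does not forbid it.
- **That a known readmission or death drops out because the telephone goes unanswered.** It must be reported.
- **That every hospitalization or death is a missed endpoint event.** Safety counts only related SAEs, with the 7-day bleeding exclusion; effectiveness counts only delayed bleeding or failed closure.
- **That 3 to 4 unseen failures added to an expected 13 would reach the 16/17 boundary and endanger the trial.** That boundary belongs to 217 subjects; on 240 the limit is 18.
- **That all 23 could be recovered.** Section 10.2 bars further data on most who withdraw.

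The defence does not close the gap. The effort in 10.3 is aimed at reaching the participant, not at establishing the outcome. The duty in 19.4 starts with awareness, and nothing requires the site to look. Lost to follow-up is itself an accepted reason for non-completion, and monitor review is not tied to close-out.

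**Conclusion.** The point holds in limited form. No section of either document requires a record or vital-status check before a subject is deemed lost, so endpoint events that the site has not become aware of may be missed, and such loss may depend on outcome.

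The exposure lies near the performance goals, not at the expected rates. With up to 23 of 240 lost and true success at 89%, complete-case type I error rises from 4.9% to about 11% or 24% if the lost fail at 20% or 30%; safety behaves similarly. These figures rest on assumed event rates among the lost, on the whole attrition allowance being unreachable subjects, and on none of their events being otherwise known to the site. They are therefore upper-end illustrations, not forecasts. If loss is unrelated to outcome there is no inflation.

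This is an inexpensive improvement to the plan. It is not a flaw that invalidates the design.

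**What to change.** Amend Protocol 10.3 and 11.7. Before a subject who has not withdrawn consent is declared lost, the site reviews its own medical record and, where the ICF permits, contacts the referring physician or a named alternate contact. It looks for bleeding, re-intervention, readmission or death through day 30. Any event is entered in the EDC with the source marked as record review. In the SAP, report both primary endpoints with and without outcomes known only from records.

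As a clerical matter, align the 10.3 wording about returning for visits with the telephone interview. Section 8.1 already lists that interview as a study visit, so the meaning does not change.

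The cost is an amendment, ICF wording, and a chart check by existing staff for at most about 23 subjects. Sample size, tests and critical values stay as planned. Observed rates may be slightly less favourable, and events treated elsewhere may still be missed.
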